3.3.2 Exclusion Criteria

Subjects meeting any of the following exclusion criteria at screening should not be considered as eligible to participate to the study:

 Participation in previous clinical trials for AD and/or for neurological disorders using active immunization unless there is documented evidence that the subject was treated with placebo only and the placebo vaccine is not expected to induce any specific immune response. 📿 AC Immune

- 2. Participation in previous clinical trials for AD and/or for neurological disorders using any passive immunization within the past 6 months (or 5 half-lives of the investigational antibody, whichever is longer) prior to screening unless there is documented evidence that the subject was treated with placebo only and the placebo is not expected to induce any specific immune response.
- 3. Participation in previous clinical trials for AD and/or for neurological disorders using any small molecule drug including BACE-1 inhibitors within the past 3 months prior to screening.
- 4. Concomitant participation in any other clinical trial using experimental or approved medications or therapies.
- 5. Presence of positive ANA titers at a dilution of at least 1:160 in subjects without clinical symptoms of auto-immune disease.
- 6. Current or past history of auto-immune disease, or clinical symptoms consistent with the presence of auto-immune disease.
- 7. Immune suppression including but not limited to the use of immunosuppressive drugs or systemic steroids unless they have been prescribed transiently more than 3 months prior to screening.
- 8. History of severe allergic reaction (e.g., anaphylaxis) including but not limited to severe allergic reaction to previous vaccines and/or medications.
- 9. Prior history of clinically significant hypoglycaemic episodes.
- 10. Drug or alcohol abuse or dependence currently met or within the past five years according to DSM-V criteria.
- 11. Any clinically significant medical condition likely to interfere with the evaluation of safety and tolerability of the study treatment and/or the adherence to the full study visit schedule.
- 12. Any clinically significant medical condition likely to impact the immune system (e.g, any history of acquired or innate immune system disorder).
- 13. Use of hydralazine, procainamide, quinidine, isoniazide, TNF-inhibitors, minocycline within the last 12 months prior to screening.
- 14. Use of diltiazem unless on a stable dose for at least 3 months prior to screening.
- 15. Significant risk of suicide defined, using the Columbia-Suicide Severity Rating Scale, as the subject answering: "yes" to suicidal ideation questions 4 or 5 or answering: "yes" to suicidal behavior within the past 12 months.
- 16. Concomitant psychiatric or neurologic disorder other than those considered to be related to AD (e.g. head injury with loss of consciousness, symptomatic stroke, Parkinson's disease, severe carotid occlusive disease, TIAs).
- 17. History or presence of uncontrolled seizures. If history of seizures, they must be well controlled with no occurrence of seizures within 2 years prior to screening. The use of anti-epileptic medications is permitted if at stable dose for at least 3 months prior to screening.
- 18. History of meningoencephalitis within the past 10 years prior to screening.
- 19. Subjects with a history of hemorrhagic and/or non-hemorrhagic stroke.
- 20. Presence or history of peripheral neuropathy.
- 21. History of inflammatory neurological disorders with potential for CNS involvement.
- 22. Screening MRI scan showing structural evidence of alternative pathology not consistent with AD which could cause the subject's symptoms. Evidence of space occupying lesions other than benign meningioma of less than 1 cm diameter, more than two lacunar infarcts or one single infarct larger than 1 cm in diameter or any single area of superficial siderosis or evidence of a prior macro-hemorrhage ≥10 mm. Microbleeds on T2* MRI are allowed up to a maximum of 10, regardless of the location.
- 23. MRI examination cannot be done for any reason, including but not limited to metal implants contraindicated for MRI studies and/or severe claustrophobia.
- 24. Significant hearing or visual impairment or other issues judged relevant by the investigator preventing to comply with the protocol and to perform the outcome measures.

📿 AC Immune

- 25. Clinically significant infections or major surgical operation within 3 months prior to screening. Planned surgery anticipated to occur during participation in the study must be reviewed and approved by the medical monitor at screening.
- 26. Any vaccine received within the past 2 weeks before screening, including influenza vaccine.
- 27. Clinically significant arrhythmias or other clinically significant abnormalities on ECG at screening.
- 28. Myocardial infarction within one year prior to baseline, unstable angina pectoris, or significant coronary artery disease.
- 29. History of cancer within the past 5 years other than treated squamous cell carcinoma, basal cell carcinoma and melanoma in situ, or in-situ prostate cancer or in-situ breast cancer which have been fully removed and are considered cured.
- 30. Clinically significant deviations from normal values for hematologic parameters, liver function tests, and other biochemical measures, that are judged to be clinically significant in the opinion of the investigator.
- 31. Pregnancy confirmed by blood test at screening, or subject planning to be pregnant or lactating.
- 32. Receipt of any anticoagulant drug or antiplatelet drug, except aspirin at doses of 100 mg daily or lower (in order to avoid risk of bleeding during scheduled or unscheduled lumbar puncture).
- 33. Receipt of any antipsychotic drugs unless on stable low doses for the treatment of insomnia.
- 34. Donation of blood or blood products within 30 days prior to screening or plans to donate blood while participating in the study.
- 35. Positive VDRL consistent with active syphilis at screening.
- 36. Positive HIV test at screening.
- 37. Laboratory or clinical evidence of active hepatitis B and/or C at screening.
- 38. Serum creatinine greater than 1.5x upper limit of normal, abnormal thyroid function tests or clinically significant reduction in serum B12 or folate levels (note: all oral doses of thyroid replacement agents, B12 or folate have to be stable for at least 3 months prior to screening).

3.3.3 Removal of Subjects from Therapy or Assessment

A subject will be considered to have completed the study when he or she completes the Visit 11 at Week 74 (or the Visit 13 at Week 98 in case of optional post-injection period extension). If a subject is discontinued at any time after randomization into the study, the investigator will make every effort to follow the subject and complete the premature discontinuation assessments as shown in Section 3.5.3.

Additional participants may be recruited to replace withdrawn subjects unless the subject withdrew for safety reasons.

A termination electronic case report form (eCRF) page should be completed for every subject who received investigational product, whether or not the subject completes the study. The reason for any early discontinuation should be indicated on this form.

The primary reason for a subject discontinuing early should be selected from the following standard categories of early termination:

- Adverse Event (Adverse Reaction): Clinical or laboratory events occurred that, in the medical judgement of the investigator for the best interest of the subject, are grounds for discontinuation. This includes serious and non-serious adverse events (AEs) regardless of relation to the investigational product.
- Death: The subject died.
- Withdrawal of Consent:

🕜 AC Immune

- The subject or caregiver desired to withdraw from further participation in the study in the absence of an investigator-determined medical need to withdraw. If the subject gave a reason for withdrawing, it should be recorded in the eCRF. In case of caregiver withdrawal, the subject can continue in the study if a new caregiver consents to act in this role.
- In the Netherlands, subjects who become unable to maintain their decisional capacity during the course of the study as assessed with the MacCAT-CR interview (refer to section 3.5.6 and 6.1.3).
- Protocol Violation: The subject's findings or conduct failed to meet the protocol entry criteria or failed to adhere to the protocol requirements (e.g., drug noncompliance, use of prohibited concomitant treatment (section 3.4.7.2), failure to return for a defined number of visits). The violation is important enough to justify early discontinuation since it would hamper the evaluation of the primary endpoints of the study.
- Lost to Follow-up: The subject stopped coming for subsequent study visits and study personnel were unable to contact the subject.
- Other: The subject was discontinued for a reason other than those listed above, such as termination of study by sponsor.

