3.1.5 Safety follow-up

All subjects will be kept under clinical observation for 24 hours after the first administration of study vaccine and for 4 hours after subsequent administrations of study vaccine. During that period, the vital signs will be monitored and the injection site will be observed on a regular basis. A physical examination will be performed prior to discharge. The clinical observation may be prolonged in case of safety concerns according to the clinical judgement of the investigator. A subsequent safety assessment will also be performed 48 to 72 hours after each immunization by telephone call for all study subjects. For adverse events considered possibly or probably related to the study vaccine of greater than mild severity according to investigator assessment, subjects will be required to return to the clinic for additional safety assessment. In each sub-cohort, the first dosing of the first 4 subjects should be performed. This will allow the site principal investigator to assess whether there is any clinically relevant safety issue related to study vaccine prior to

dosing the subsequent subject. Safety laboratory samples will be collected at baseline, prior to each injection and 2-4 weeks after each injection. Laboratory results will be reviewed by the Medical Monitor on a periodic basis including all out of range values.

All treated subjects will have a safety follow-up period of 24 weeks (6 months) after the end of the treatment period. During this period, subjects will be asked to attend a first follow-up visit 19 weeks after the last administration and a last visit at the end of the follow-up period (26 weeks after the last administration).

Additionally to the monitoring and recording of the AEs throughout the course of the study and the reporting of SAEs, participant safety will be monitored throughout the study with regular review of safety data by a Data and Safety Monitoring Board (DSMB). The DSMB will consist of specific experts in the field, who will meet on a regular basis to review the safety data of the participants. The outcome of the DSMB meeting will be registered in minutes and will include a recommendation as to whether to continue the study as planned or to modify or stop the study. The DSMB's responsibilities and activities will be described in a charter.

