3.2.3 Follow-up Period

Subjects participating in the study will be followed up for 24 weeks starting 2 weeks after the last study vaccine administration (treatment completion or early termination). The follow-up period will consist of on-site visits 19 weeks and 26 weeks (6 months) after the last administration.

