3.5.2.23 Unscheduled Visit (UV)

At any time during the study, subjects might be invited to the site for additional visits (e.g. further evaluation needed following a phone call with the subject). In case of safety concerns, as per investigator assessment during a scheduled "Phone call" or a visit of the post-injection period extension (if applicable) with the subject, an additional visit will be scheduled in order to further assess the event(s). Any subjects attending an unscheduled visit should at a minimum complete the following safety related assessments:

- Provide information on new AEs/SAEs since last visit.
- Provide information on new concomitant medication since last visit.
- Be examined for the Vital signs
- Go through physical and neurological examination
- Have blood withdrawn for standard safety evaluation

Upon investigator's medical judgement, other assessments considered as needed can be performed during those visits (MRI, ECG, etc.).

Due to the resurgence of the pandemic in multiple participating countries since September 2020 and in case the subject and caregiver cannot travel to the site due to Covid-19 restriction, the Unscheduled Visit and related assessments will be performed at subject's home if feasible and locally permitted (see details under 3.5.1.1 Alternative Mode of Administration of Assessments to Reduce Safety Risks due to Participation during Covid-19 pandemic).

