3.5.3 Assessments for Premature Termination

Any subject, who withdraws from the study prior to completion (see standard categories of early termination under section 3.3.3), will be encouraged to at least complete the safety assessment evaluation (see detail under 3.5.2.21 Unscheduled Visit) by attending a last visit.

If this is not possible, subject will be asked to at a minimum, provide the reason for withdrawal and provide information on any adverse events that might have arisen since the last visit and the outcome of any previously recorded AEs.

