## 9.2 Intention-to-Treat

The intention-to-treat (ITT) population is defined as all randomized subjects who received at least one dose of the drug during the study, and will be used for presentation of primary, secondary and exploratory endpoints and for description of baseline characteristics.

The ITT population will be analyzed and presented according to the treatment arm in which the subject was randomized regardless of the number of injections that the subject actually received.

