## 9.3 Per Protocol

The per-protocol (PP) population is defined as all subjects from the ITT population who do not have any important protocol deviations which might significantly affect the completeness, accuracy, and/or reliability of the study data or that may have an impact on the immune response assessment (a subset of all important protocol deviations which will be considered critical), and will be used as a supportive analysis of the primary and secondary efficacy endpoints for the final analysis.

The PP population will be defined during the course of the study ahead of each interim analysis but semiunblinded IA TFLs based on the PP analysis set will not be prepared and delivered to the Sponsor Data Review Committee in case there is a risk of unblinding. Such instances could be for example if high number of subjects missed visits and/or treatment (vaccine) administration even though this might not be considered a major protocol deviation.

Analysis based on the PP population per timepoint might also be presented. This will allow to include all the participants in the summary tables and figures who do not have any major protocol deviations that are expected to impact the immunogenicity outcomes up to a corresponding timepoint.

All the protocol deviations will be identified and recorded in the Predictivv Study Operation (PSO) system. The subset of important protocol deviations leading to exclusion from the PP set will be identified prior to the unblinding of the study for the final analysis and will include at least the following:

- Subjects who entered the study even though they did not satisfy the eligibility criteria
- Those who developed withdrawal criteria during the study but were not withdrawn
- Those who received the wrong treatment or incorrect dose
- Those who received any excluded concomitant treatment, see further details below

Subjects receiving acetylcholinesterase inhibitor and/or memantine should have been on a stable dosage for at least 3 months prior to baseline.

The following treatments are not permitted throughout the study:

- Anticoagulants or antiplatelet drugs, except aspirin at doses of 100 mg daily or lower
- Standard of care immunizations during the period ranging from 2 weeks before or after any administration of study vaccine to avoid potential interference
- Hydralazine, procainamide, quinidine, isoniazide, TNF-inhibitors, minocycline
- Diltiazem unless subject is on stable dose 3 months prior to screening

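### Protocol 3.3.3 lets a violation end study participation, and the exit rules contradict the follow-up rules, so later titer and safety data on violators can be missing from the ITT summaries

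*Protocol*

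**What the plan says.** Protocol 3.3.3 gives the standard reasons for early discontinuation. One is protocol violation, which covers failed entry criteria, noncompliance, a prohibited treatment and missed visits. It adds: "The violation is important enough to justify early discontinuation since it would hamper the evaluation of the primary endpoints of the study". For any discontinuation after randomization, the same section says that "the investigator will make every effort to follow the subject and complete the premature discontinuation assessments as shown in Section 3.5.3".

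Section 3.5.3 says that a withdrawing subject "will be encouraged to at least complete the safety assessment evaluation" at one last visit, using the Unscheduled Visit list. It cites 3.5.2.21 for that list, but 3.5.2.21 is Visit 12; the Unscheduled Visit is 3.5.2.23. The minimum content there is adverse events, medications, vital signs, physical and neurological examination, and "Have blood withdrawn for standard safety evaluation". Titers, MRI and cognitive scales are not on the list; further tests are left to the investigator's judgement. Section 4 ends the safety reporting period at the last visit or assessment when a subject terminates early.

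Other sections promise more:

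- Protocol 3.1.5: "All treated subjects will have a safety follow-up period of 24 weeks (6 months) after the end of the treatment period".
- Protocol 3.2.3: subjects "will be followed up for 24 weeks starting 2 weeks after the last study vaccine administration (treatment completion or early termination", with on-site visits 19 and 26 weeks after the last injection.
- Protocol 3.1.1: subjects with fewer than four injections, whatever the reason, are followed at least as long after their last one. SAP 6.0 repeats this and adds Week 74 as the end.

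On analysis, SAP 9.2 states: "The ITT population will be analyzed and presented according to the treatment arm in which the subject was randomized regardless of the number of injections". SAP 9.3 takes out of the per-protocol set those who failed eligibility, those given a wrong treatment or dose, and "Those who received any excluded concomitant treatment, see further details below".

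**The concern.** The stated ground for ending participation is to protect the primary endpoints; it is not the subject's safety. An ITT analysis is meant to keep such subjects and their data, and the per-protocol set already exists to show results without them. If violators leave the study, their later samples are never taken, and an ITT rule about who is analysed cannot recover them.

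Two things are at stake. Late titer summaries, the responder rate and AUC may rest mainly on adherent subjects in very small groups, and the observed response rate also informs sub-cohort expansion (3.1.4). In addition, a vaccinated subject may not have the later safety visits, depending on which section the site follows.

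**Working it through.** **1. The plan's own figures.** The only sizing figures are for safety with 6 active subjects (Protocol 5.3.1). The chance of seeing an event of rate p is 1 − (1 − p)^6:

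- p = 1%: 5.85% (stated 6%)
- p = 10%: 46.86% (stated 47%)

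The upper bound when no event is seen, at confidence c, is 1 − (1 − c)^(1/6):

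- c = 80%: 23.5% (stated 24%)
- c = 90%: 31.9% (stated 32%)

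All four reproduce. They count 6 subjects as observed.

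**2. The two sets of rules side by side.** Under 3.5.3, and Section 4 read with it, a terminated subject owes one encouraged visit with safety content only, and reporting ends there. Under 3.2.3, the same subject attends two further on-site visits over 24 weeks. Under 3.1.1 and SAP 6.0, a subject short of four injections is followed for at least that long. No passage says which prevails.

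**3. What 3.2.3 would still miss.** With the last injection at week L, the visits fall at L + 19 and L + 26:

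- L = 0: Weeks 19 and 26
- L = 8: Weeks 27 and 34
- L = 24: Weeks 43 and 50
- L = 48: Weeks 67 and 74

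Protocol 5.3.6.2 names Week 50 for the primary change from baseline. It is not covered when the last injection was at Week 0 or Week 8. With a last injection at Week 24, the second visit falls on Week 50, but nothing follows, so an AUC to Week 74 is incomplete. SAP 6.0 would carry follow-up to Week 74 but does not say which visits or samples that means.

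**4. What is lost if only 3.5.3 is applied.** SAP 11.6.1 lists 14 scheduled post-baseline titer visits (Weeks 2, 8, 10, 15, 20, 24, 26, 31, 36, 42, 48, 50, 67, 74). Leaving after Week 8 loses 12, after Week 24 loses 8, and after Week 48 loses 3.

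**5. Handling of the gaps.** SAP 8.14 imputes only titers below the quantification limit. SAP 8.20 gives the trapezoidal rule without saying what to do when a subject's curve stops early. Neither document has a rule for missed titer visits.

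**6. Size in a group of 6.** One subject is 1/6 = 16.7%. For illustration, if the lost subject is the only non-responder, 5/6 = 83.3% becomes 5/5 = 100%. For safety, the extreme case is a subject who contributes nothing: with n = 5, the chance of seeing a 10% event is 1 − 0.9^5 = 41.0% (against 46.9%), and the 80% and 90% bounds become 27.5% and 36.9%. This overstates the loss, because a removed subject does contribute up to exit.

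**7. How often.** The documents give no rate. Assuming 2%, 5% or 10% per subject, the chance that at least one of 6 leaves this way is 1 − (1 − q)^6 = 11%, 26% or 47%.

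**The case against.** The sentence in 3.3.3 defines a category for recording why a subject stopped, and applies only to violations judged important. It does not order removal at every violation. The plan expects violators who stay: Protocol 5.3.3 has a deviation category for subjects who met withdrawal criteria but were kept, SAP 8.6 uses 3 of 4 injections (75% compliance) as its worked example, and 7 of 8 subjects in sub-cohort 1.1 missed the third injection yet still had Week 50 summaries planned (SAP 12.0). The exit list is a minimum. Visits 10 and 11 collect titers, and Visit 11 adds MRI and the cognitive and clinical scales, so applying 3.2.3 would recover some of the late data.

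All of this stands, and it defeats a stronger reading that a reader might infer: that titers and safety follow-up stop at the violation and the ITT analysis becomes partly per-protocol. Follow-up after early termination is provided for in several places. Removed subjects remain in ITT with their data up to exit, whereas the per-protocol set drops them altogether, since Protocol 5.3.2 counts withdrawal as a major deviation. The two analyses can still differ. Nor do the documents link these violations to weak response; much of the prohibited list in 3.4.7.2 consists of anticoagulants, antiplatelets and cardiovascular drugs.

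The objection does not resolve the contradiction between the exit rules and the follow-up rules, and it does not supply a Week 50 sample for a subject who stops after the first or second injection.

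**Conclusion.** The point holds as a contradiction in the follow-up rules with a possible missing-data bias. A site can follow 3.5.3 and collect no further titer, or follow 3.2.3 and still miss Week 50 when the last injection was at Week 0 or Week 8. Late ITT titer summaries and AUC may then lack violators, with no stated rule for the gap.

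One loss is 17% of an active group of 6. The move from 83% to 100% is a constructed illustration that assumes one removal, who is also the only non-responder. The number of removals is not stated, and the direction of any bias cannot be established from the documents. Titers are descriptive with no planned testing, so no type I error or power is affected. It merits correction because these groups are small and removal is unnecessary for the analysis: SAP 9.3 already provides the exclusion from the per-protocol set.

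**What to change.** In 3.3.3, separate stopping injections from leaving the study. The protocol already makes this distinction in 3.5.4, where anti-dsDNA-positive subjects with symptoms stop immunization and stay in safety follow-up. State that:

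- a protocol violation alone does not end study assessments;
- unless consent is withdrawn, the subject keeps the scheduled titer and safety assessments to Visit 11;
- the subject stays in the ITT and Safety sets, and the violation is handled through the per-protocol set.

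Whether injections continue stays with the existing rules.

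Reconcile 3.3.3, 3.5.3 and Section 4 with 3.1.1, 3.1.5, 3.2.3 and SAP 6.0, and correct the reference in 3.5.3 from 3.5.2.21 to 3.5.2.23.

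The cost is protocol wording. The visits are already scheduled; a few subjects attend visits they would otherwise have missed.
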